9.1.1. Primary Design - Comparative Cohort Design

A comparative cohort design will be used to estimate incidence rates and incidence rate ratios of prespecified outcomes among immunocompromised, or renally impaired, or hepatically impaired older adults with and without receipt of the ABRYSVO vaccine. Individuals in the unvaccinated cohort must have no record of an RSV vaccine on the index date or in the baseline period prior to index date or any other vaccine on the index date but can later receive ABRYSVO and enter the vaccinated cohort if all eligibility criteria are met. To address possible selection bias due to health seeking behaviours, unvaccinated individuals will be randomly selected from a population of patients who have regular use of preventive medical care, defined as at least one vaccination record in the year prior to the index date. The baseline period is defined as 12 months prior to the index date. The follow-up period will begin from day 1 (the day after ABRYSVO administration for vaccinated cohort, or the day after matched index date for the unvaccinated cohort) and continue to the earliest occurrence of an outcome, date of RSV vaccination (for unvaccinated individuals who later receive any RSV vaccine only), the end of administrative follow-up, end of the study period, or death. For those outcomes with a defined risk window, follow-up will also be truncated at the end of the risk window. To enhance comparability between the vaccinated and unvaccinated cohorts, ATT weights will be used. Weights, based on PS, will incorporate additional measures of healthcare utilization in the baseline period to further account for potential differences in healthcare seeking behaviour between the vaccinated and unvaccinated cohorts. However, as this study focuses on patients with chronically managed conditions, differences in healthcare seeking behaviour are not anticipated. IPCW will also be employed if informative censoring (i.e., differential rates of censoring during follow up) and high censoring rates are observed between the vaccinated and unvaccinated cohorts. Examples of patient follow-up scenarios are depicted in Figure 1 and Figure 2. Comparative analyses will also include variables that remain inadequately balanced between the two cohorts in a doubly robust approach. Further details are provided in Section 9.7.2 and Section 9.7.3.

Figure 1 Comparative Cohort Design

[figure not shown]

Notes:

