9.2.1.1. Immunocompromised Population

Individuals must meet at least one of the following criteria at index date or in the 12-month baseline period prior to the index date (unless otherwise specified) to be eligible for inclusion in the immunocompromised population. Definitions will be aligned as closely as possible across participant data sources. Definitions may be modified if certain data elements are not available or are incompletely captured in some data sources.

- Diagnosed with a primary immunodeficiency/immune dysregulation disorder, also known as inborn errors of immunity, as defined by the European Society for Immunodeficiencies (ESID) Registry,²⁴ at any point in medical history
- Diagnosed with HIV/AIDS
- Diagnosed with hematologic malignancy (e.g., chronic lymphocytic leukemia, non-Hodgkin lymphoma, multiple myeloma, acute leukemia) with evidence of treatment at any point in medical history
- Diagnosed with solid malignancy with evidence of treatment within the last 5 years
- Diagnosed with rheumatologic/inflammatory conditions (e.g., Sjogren's syndrome, SLE, psoriatic arthritis, rheumatic arthritis, arthritis spondylarthritis, polymyalgia rheumatica, demyelination multiple sclerosis, polymyalgia rheumatica, IBD, autoimmune thyroiditis) and have evidence of treatment with chemotherapy, immune modulators, or high-dose or long-term systemic corticosteroids (>3 months) in the last 12 months
- Solid-organ transplant recipients or islet transplant recipients taking immunosuppressive therapy
- CAR-T-cell therapy or hematopoietic stem cell transplant recipients taking immunosuppressive therapy
- Active treatment with various immunosuppressive agents (e.g., high-dose systemic corticosteroids [20 or more mg of prednisone or equivalent per day when administered for 2 or more weeks] or long term systemic corticosteroid use (>3 months), alkylating agents, antimetabolites, transplant-related immunosuppressive drugs, cancer chemotherapeutic agents classified as severely immunosuppressive, TNF blockers, and other biologic agents that are immunosuppressive or immunomodulatory, active treatment with ATC code L04).

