9.2.2. Exclusion Criteria

Patients meeting any of the following criteria will not be included in the study:

- 1. Have a diagnosis for the specific outcome under study within the 12 months prior to the index date (to distinguish the recording of previous events from true new events) and at any time prior to the index date for diabetes type 1
- 2. Have received any RSV vaccinations during the 12-month baseline period

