a. Day 0 is the date of vaccine administration (i.e, index date for the vaccinated cohort in the comparative cohort design and SCRI design) or matched index date (for the unvaccinated cohort in the comparative cohort design) b. To align with ongoing postmarketing study C3671031, A Post-Authorization Safety Study of Guillain-Barré Syndrome (GBS) Following ABRYSVOTM Among Older Adults in the United States, sensitivity analyses will be performed for GBS, acute disseminated encephalomyelitis, and transverse myelitis using shorter risk intervals of 1-21 days, 5-28 days, and 1-21 days, respectively. Further details are outlined in Section 9.7.4. c. Published risk and control intervals for demyelinating diseases and cranial disorders were applied to transverse myelitis and narcolepsy/cataplexy.

d. Please note that alternative risk windows were reported in other studies.

e. To align with ongoing postmarketing study C3671037, A Post-Authorization Safety Study of Atrial Fibrillation Following Respiratory Syncytial Virus Vaccine (ABRYSVOTM) Among Older Adults in the

PFIZER CONFIDENTIAL

CT24-WI-GL02-RF02 5.0 Non-Interventional Study Protocol Template For Secondary Data Collection Study 01-Aug-2023

Page 31 of 72

Table 1	List of Select Adverse Events of Special Interest
---------	---

Body system/	Adverse event of special interest	Estimated risk	Analytic Approach
classification		window (days) ^a .	

Veterans Affairs Health System, sensitivity analysis will be performed for atrial fibrillation and supraventricular arrhythmias using a shorter risk interval of 0-3 days. Alternative risk intervals of 0-1 day or 0-30 days may also be considered. Details are provided in Section 9.7.4.

f. Similar risk and control intervals were applied to all cardiovascular and haematological disorders characterised by damage to the blood vessels and/or arteries and clotting (i.e, coagulation disorders and single organ cutaneous vasculitis).

g. Risk intervals for most outcomes start on Day 1 post-index, but for some outcomes, the risk interval starts on the day of vaccination due to biological plausibility of rapid onset following vaccination.

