9.3.2.2. Outcome Identification

Outcomes will be identified in participant data sources with algorithms based on codes for diagnoses, procedures, and treatments. Proposed algorithms and diagnostic codes for all prespecified outcomes will incorporate definitions developed by the ACCESS project⁴² and will be described in more detail in the statistical analysis plan (SAP). ACCESS developed harmonised definitions and code lists for the outcomes listed in **Table 1**. for application to routine healthcare data sources across Europe. These definitions were subsequently used for the calculation of background outcome rates to contextualize emerging COVID-19 vaccine safety data. Healthcare data covering approximately 130 million lives across 7 European countries and 22 data sources were used to generate background rates. Algorithms will be tailored to the data source and will consider the provenance of the medical records that have identified the outcome, e.g., primary care, access to hospital care, and access to emergency care.⁴³ Multiple algorithms for the same outcome may be included in the analysis, to assess the potential impact of differential misclassification. Several outcomes have been validated in previous VAC4EU studies.

Outcome onset will be primarily defined as the date of the healthcare encounter associated with the relevant diagnostic code. Most outcomes of interest are serious enough to warrant healthcare consultation close to the time of symptom onset. However, for those outcomes that might include a lag between the onset of symptoms and diagnosis in a healthcare setting (e.g., DVT or diabetes type 1), algorithms may incorporate additional considerations to capture onset dates closer to the time of symptom onset. These considerations will be detailed in the SAP. Sensitivity analyses may also be incorporated to assess assumptions around outcome onset for relevant outcomes.

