Individuals will be followed from the index date until death, end of administrative follow up (and/or risk interval), end of the study period, or the date of ABRYSVO/RSV vaccination (for unvaccinated individuals who later receive any RSV vaccine only), whichever occurs first. The degree of loss to follow-up will be examined. If the censoring rates differ by exposure group (i.e, indicating informative censoring) and high censoring rates (e.g., >20%) are observed, IPCW will be derived to account for informative censoring, where the weight will be calculated for each individual as the inverse of the probability of remaining uncensored during the risk interval. The stabilized IPCW will be calculated as follows, where A= vaccination, V = covariates to adjust, and C=0 represents that the patient has remained uncensored: (Pr[C=0 | A=1])/(Pr[C=0 | A=1,V=v]) for the vaccinated cohort; (Pr[C=0 | A=0])/(Pr[C=0 | A=0,V=v]) for the unvaccinated cohort.

The final weights will be calculated as the product of the ATT weight and IPCW (ATT x IPCW) if informative censoring is observed, and the ATT weight will be used as the final weight if informative censoring is not observed. The distribution of final weights (e.g., mean, SD, minimum, and maximum values) will be examined and extreme weights will be truncated or capped at the 1st and 99th percentile. After weighting, the distribution of baseline characteristics will be evaluated between the vaccinated cohort and the unvaccinated cohort, and variables that remain inadequately balanced (standardized difference >10%) between the two cohorts will be included as regression model covariates in a doubly robust approach.

Weighted Poisson regression models will be conducted to calculate IRRs of outcomes among vaccinated cohort vs. unvaccinated cohort. Incidence rate ratios will be summarized, and robust variance estimators will be used to calculate the corresponding 95% CIs.

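### Day 0 lies in neither the outcome look-back nor the Day 1 follow-up for most outcomes, so a repeat code of an event first recorded at index can count as new

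*Protocol*

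**What the plan says.** **Look-back.** Protocol 9.2.2 excludes people who "Have a diagnosis for the specific outcome under study within the 12 months prior to the index date"; for type 1 diabetes the look-back is any time before index. The stated aim is "to distinguish the recording of previous events from true new events". Section 9.1.1 ends the baseline period at the same point: "The baseline period is defined as 12 months prior to the index date".

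**Start of observation.** Section 9.1.1: "The follow-up period will begin from day 1 (the day after ABRYSVO administration for vaccinated cohort", with the corresponding day for comparators. Section 9.1.2 starts the SCRI risk interval on Day 1 and puts the control interval after it. Note g to Table 1: "Risk intervals for most outcomes start on Day 1 post-index", with some outcomes starting on Day 0.

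**Dating of events.** Section 9.3.2.2: "Outcome onset will be primarily defined as the date of the healthcare encounter associated with the relevant diagnostic code".

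**Text that points the other way.** Section 9.7.3.1 says "Individuals will be followed from the index date until death", and Section 9.7.2 measures time to onset from the index date.

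**The concern.** Where the protocol wants the index date included, it says so. The immunocompromised population is assessed "at index date or in the 12-month baseline period prior to the index date", Section 9.1.1 rules out an RSV vaccine for comparators both at index and in the baseline period, and Section 9.3.3 reads covariates at index or in the baseline period. Exclusion 1 has no such wording, so its reference to time before the index date cannot simply be taken to include Day 0.

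A person whose outcome is first coded on Day 0 is then not excluded, has no event counted on Day 0, and is at risk on Day 1. A discharge record or follow-up visit coded a few days later has its own encounter date and can be counted as a new event. That is the error exclusion 1 was written to prevent. The effect is largest in the short windows, where a few misdated events form a larger share of the total.

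**Working it through.** **1. How many outcomes are affected.** Table 1 has 26 outcome rows. Three have a window starting on Day 0: generalised convulsion (0–42), anaphylaxis (0–1) and death (0–365). That leaves 26 − 3 = 23 starting on Day 1. Fifteen rows are marked for SCRI; two of these (convulsion, anaphylaxis) start on Day 0, leaving 13.

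**2. Direction in the SCRI.** The risk interval directly follows Day 0 and the control interval comes later. Repeat codes of a Day-0 case that cluster soon after Day 0 fall mainly in the risk interval, so any bias is upward.

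**3. Direction in the cohort.** This depends on whether Day-0 coding is higher in vaccinees, because they have a contact that day, or lower, because people who are unwell defer vaccination (a possibility raised in Section 9.7.4).

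**4. Size, as an illustration.** The documents give neither Day-0 coding rates nor re-coding shares, so these inputs are assumptions. Let the true ratio be 1 and the outcome rare, with one unit of true events per day. W is the window in days. k is Day-0 coding in vaccinees relative to an ordinary day, with comparators at 1. p is the share of Day-0 cases re-coded within the window, and p2 the share first re-coded in an equal-length control interval.

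- Cohort IRR = (W + k·p) / (W + p)
- SCRI IRR = (W + k·p) / (W + k·p2)

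| W | p | p2 | Cohort, k = 10 | SCRI, k = 10 | SCRI, k = 1 |
|---|---|---|---|---|---|
| 7 | 0.25 | 0.10 | 9.5/7.25 = 1.31 | 9.5/8.0 = 1.19 | 7.25/7.10 = 1.02 |
| 14 | 0.35 | 0.12 | 17.5/14.35 = 1.22 | 17.5/15.2 = 1.15 | 14.35/14.12 = 1.02 |
| 28 | 0.45 | 0.12 | 32.5/28.45 = 1.14 | 32.5/29.2 = 1.11 | 28.45/28.12 = 1.01 |
| 42 | 0.50 | 0.12 | 47/42.5 = 1.11 | 47/43.2 = 1.09 | 42.5/42.12 = 1.01 |
| 365 | 0.80 | – | 373/365.8 = 1.02 | – | – |

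At k = 1 the cohort ratio is exactly 1. At k = 0 (complete deferral) it is 7/7.25 = 0.97 at 7 days and 42/42.5 = 0.99 at 42 days, and the SCRI ratio is 1.00.

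The outer edge of the range is p = 1 and p2 = 0 at 7 days. The SCRI ratio is then 8/7 = 1.14 at k = 1 and 17/7 = 2.43 at k = 10, and the cohort ratio at k = 10 is 17/8 = 2.13.

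**5. Scale for a rare outcome.** The protocol's own 42-day background for GBS reproduces: 6/100,000 ÷ 365 × 42 = 0.0000069. Its inverse is about 145,000, so one false event per 145,000 vaccinees would equal the whole expected background. The sample sizes in Table 2 do not bear on this point.

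**The case against.** The strongest reply is that a repeat code becomes a false event only under a particular algorithm. Section 9.3.2.2 leaves the algorithms to the SAP, and a first-code-on-record rule would remove the artefact. This stands, and the conclusion is conditional on it. Eligibility, however, is fixed in the protocol and should not depend on a rule not stated there.

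The second reply is that Section 9.7.3.1 follows people from the index date, so a Day-0 code might itself be the event. That reading contradicts Section 9.1.1 and the Day-1 windows in Table 1. It shows that the handling of Day 0 is unsettled rather than closing the gap.

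A reader might infer that the false events fall mostly among vaccinees. The documents do not establish this. Deferral when unwell works against it, and in SNDS the index is a pharmacy dispensing date with no injection date held (Section 9.4.5), so a dispensing contact need not produce a diagnosis code. A reader might also assume 12 coded contacts a year, take k as about 365/12 ≈ 30, and arrive at a 7-day cohort ratio of (7 + 30 × 0.25)/7.25 = 2.00. The protocol gives no contact frequency, and nothing in it suggests that acute events such as myocarditis with pericarditis are typically first coded at a planned vaccination visit.

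Some planned checks could reveal part of the problem: narrow and broad algorithms, a pre-vaccination control interval and negative control outcomes (Section 9.7.4). None is aimed at Day 0. If repeats cluster early, the shorter 1–21 day intervals for GBS and transverse myelitis would enlarge the effect.

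**Conclusion.** The gap is in the text and holds for 23 of 26 outcome rows and 13 of 15 SCRI rows. It allows, but does not by itself produce, false incident events; that requires an algorithm that accepts a repeat code. Given such an algorithm and some Day-0 cases, the SCRI bias is upward and the cohort bias can have either sign.

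The size cannot be determined from the documents. With the assumed re-coding shares it is about 2% or less when Day-0 coding is ordinary, and about 2% for 365-day windows even at 10-fold coding. At 10-fold coding the null cohort ratio is about 1.3 at 7 days and 1.1 at 42 days. These figures show sensitivity and are not estimates. The change is worth making because it costs little and the short windows are the most exposed.

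**What to change.** Tie exclusion 1 to the window of each analysis rather than to the outcome:

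- For each analysis whose risk window starts on Day 1, in the cohort and the SCRI, exclude a diagnosis *on the index date or within the 12 months before it* (for type 1 diabetes, *on or at any time before the index date*).
- For each analysis whose window starts on Day 0, end the look-back on the day before index. These are anaphylaxis, generalised convulsion, death, and the 0–1, 0–3 and 0–30 day analyses of atrial fibrillation and supraventricular arrhythmia (Table 1 note e; Section 9.7.4). A rule set by outcome would remove the Day-0 cases that those arrhythmia analyses need, because arrhythmia is printed as 1–365.

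In the same edit, reconcile Section 9.7.3.1 (followed from the index date) with Section 9.1.1 (from Day 1), and reconcile the Day-0 note g attached to arrhythmia with its printed window.

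The cost is a few words in Section 9.2.2 and one date comparison in the program. No countable Day-0 event is lost, because Day-0 codes already lie outside the Day-1 windows. No stated sample size, power or alpha changes.

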9.3.2. Outcome Definitions

9.3.2.1. Safety Outcomes

Outcomes will be defined consistently across the data sources to the fullest extent possible.

Body system/ classification	Adverse event of special interest	Estimated risk window (days) ^a .	Analytic Approach
Autoimmune diseases	Acute disseminated encephalomyelitis	1-42 ^{39, b} .	Cohort/SCRI
	Diabetes mellitus type I	1-365	Cohort
	Guillain-Barré syndrome	1-42 ^{39, b} .	Cohort/SCRI
	Narcolepsy	1-365°.	Cohort
	Thrombocytopenia (idiopathic)	$1-42^{40}$	Cohort/SCRI
	Thrombosis thrombocytopenia syndrome	1-15 ³⁹	Cohort/SCRI
Cardiovascular system ^{d.}	Acute cardiovascular injury	$1-28^{41}$	Cohort
-	Arrhythmia Specific subgroups of patients with atrial fibrillation and supraventricular arrhythmias will be identified for additional analyses	1–365 ^{e. g.}	Cohort
	Coronary artery disease	1–365	Cohort

Table 1List of Select Adverse Events of Special Interest

PFIZER CONFIDENTIAL

CT24-WI-GL02-RF02 5.0 Non-Interventional Study Protocol Template For Secondary Data Collection Study 01-Aug-2023 Page 30 of 72

Body system/	Adverse event of special interest	Estimated risk	Analytic Approach	
classification		window (days) ^a .		
	Heart failure	1–365	Cohort	
	Microangiopathy	1–365	Cohort	
	Myocarditis	1-21	Cohort/SCRI	
	Myocarditis and pericarditis	1-7	Cohort/SCRI	
	Pericarditis	1-14	Cohort/SCRI	
	Stress cardiomyopathy	1-365	Cohort	
Cinculatory		1-303 $1-28^{39, f.}$	Cohort/SCRI	
Circulatory	Coagulation disorders: Disseminated intravascular	1-20	Conort/SCRI	
system				
	coagulation, venous			
	thromboembolism (pulmonary			
	embolism, deep vein thrombosis),			
	thrombotic microangiopathy,			
	cerebral venous thrombosis,			
	thrombotic thrombocytopenia			
	syndrome, ischemic stroke,			
	myocardial infarction, haemorrhage	-		
	Single organ cutaneous vasculitis	1-28 ^{f.}	Cohort/SCRI	
	Thrombocytopenia with venous	1–15	Cohort/SCRI	
	thromboembolism			
Nerves and	Bell's palsy	1-42 ³⁹	Cohort/SCRI	
central nervous	Generalised convulsion	0-42 ^{39, , g.}	Cohort/SCRI	
system	Meningoencephalitis	1-42 ³⁹	Cohort/SCRI	
	Transverse myelitis	1–42 ^{39, b. c.}	Cohort/SCRI	
Respiratory	Acute respiratory distress syndrome	1–365	Cohort	
system				
Skin and mucous	•	1–42	Cohort	
membrane, bone				
and joints system				
Other system	Anaphylaxis	0-1 ^{39, , g.}	Cohort/SCRI	
	Death (any causes)	0–365 ^{, g.}	Cohort	

Table 1 List of Select Adverse Events of Special Interest

Notes:

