9.4.3. SIDIAP (ES)

SIDIAP was created in 2010 by the Catalan Health Institute and the IDIAPJGol Institute.⁵⁰ The database captures healthcare data collected since January 2006 during routine visits from 278 primary care centres linked to the Catalan Health Institute in Catalonia (northeastern Spain). Overall, SIDIAP covers 5.8 million people and is highly representative of the Catalan population (80%). The pseudo-anonymized health data held within SIDIAP originate from, or are linked to, various sources:

PFIZER CONFIDENTIAL CT24-WI-GL02-RF02 5.0 Non-Interventional Study Protocol Template For Secondary Data Collection Study 01-Aug-2023 Page 38 of 72

- ECAP (electronic health records in PHC of Catalan Health Institute) including comprehensive demographic information, clinical and referral events (with diagnoses captured as ICD-10 codes) registered by primary care health professionals (e.g., GPs, paediatricians, and nurses) and administrative staff in the primary care EHRs, vital signs (height, weight, body mass index, blood pressure), primary care laboratory test results, drug prescriptions issued in the PHC (captured as ATC codes), sickness leave and date of death.
- Pharmacy invoice data corresponding to the PHC drug prescriptions
- Database of diagnoses at hospital discharge

Linkages to the hospital discharge database occur on a project-by-project basis. SIDIAP includes all routine childhood and adult immunizations, including the antigen and the number of administered doses.

The SIDIAP database is updated twice per year, in January and July. The SIDIAP data have been shown to fit-for-use for epidemiological research, specifically within VAC4EU projects with respect to the characterization of use for vaccine coverage, benefits, and risk assessments.⁵⁰

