9.4.5. SNDS (FR)

The SNDS is the French nationwide healthcare database. It currently covers the overall French population (about 67 million persons) from birth (or immigration) to death (or emigration), irrespective of changes to a person's occupation or retirement status.⁵² Using a unique pseudonymized identifier, the SNDS merges all reimbursed outpatient claims from all French health care insurance schemes (SNIIRAM database), hospital-discharge summaries from French public and private hospitals (PMSI database), and the national death register.⁵² SNDS captures healthcare data from 2006 onwards and captures information on:

- Socio-demographic characteristics including gender, year of birth, and area of residence. Socioeconomic status can be derived from the presence of CMU-C (which describes full insurance coverage due to low-income status, deprivation index, and a composite indicator that gives information on patient socioeconomic status based on its geographic residence.
- **Death data** including month, year, and cause. However, there may be lags in death dates (e.g., as of January 2024, cause of death data were available to the end of 2020).
- Long-Term Disease registration with diagnoses captured with ICD-10 codes.
- Occupational accidents and diseases.
- **Outpatient reimbursed healthcare expenditures** for visits, medical procedures, nursing acts, physiotherapy, lab tests, dispensed drugs, medical devices, and transports, etc. For each expenditure, associated costs, prescriber, caregiver information (specialty, private/public practice) and the corresponding dates are provided. Indication and results are not available.
- **Inpatients encounters** capturing the primary and associated ICD-10 diagnostic codes from hospital discharge summaries with the date and duration of the hospital stay, the performed medical procedures, and the related costs. Drugs included in the DRG cost are not captured, though newer more expensive ones paid outside of DRG are available.

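### Section 9.2.2 gives only type 1 diabetes an any-time history exclusion, so other chronic outcomes left uncoded for 12 months can be counted as new

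*Protocol*

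**What the plan says.** Exclusion criterion 1 in Protocol section 9.2.2 removes people who "Have a diagnosis for the specific outcome under study within the 12 months prior to the index date". Its stated purpose and its single exception follow: "to distinguish the recording of previous events from true new events) and at any time prior to the index date for diabetes type 1". Only that one outcome gets a longer look-back.

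Table 1 (section 9.3.2.1) lists narcolepsy, "Coronary artery disease", "Heart failure" and arrhythmia, with atrial fibrillation as a named subgroup, under a 1-365 day window and the cohort approach only. Type 1 diabetes has the same window and approach. Section 9.7.2 builds the rates from incident events, and section 9.3.2.2 dates onset primarily at the encounter carrying the diagnostic code.

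Section 9.2.1 asks for at least 12 months of enrolment history and sets no upper limit. Section 9.2.1.1 already uses all of a person's history for some immunocompromise criteria.

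**The concern.** By making an exception for type 1 diabetes, the protocol accepts that 12 months is too short to separate old from new for a lifelong disease. It gives no reason why narcolepsy, which is also lifelong, is treated differently. Coronary artery disease, heart failure and chronic forms of arrhythmia raise the same question. A person diagnosed some years ago, with no code in the last 12 months, passes the exclusion and becomes a case at the next recording.

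Two reported quantities are at stake. Incidence rates are part of the primary objective (section 8.2), and false incident events inflate them. The IRR then mixes a vaccine effect on new disease with whatever ratio governs the re-recording of old disease.

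Nothing listed elsewhere repairs this. Covariates are measured at index or in the same 12 months (section 9.3.3), so the propensity score can miss the same old disease. Section 9.7.4 lists no analysis that varies the look-back.

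**Working it through.** **1. Who gets through.** Disease coded in the 12 months before index is excluded. Only established disease with no code in that year, followed by a code during follow-up, is miscounted. The data sources make such gaps plausible. In SNDS (section 9.4.5), diagnoses come from hospital discharge and long-term disease registration, and outpatient claims carry no indication. In VID (section 9.4.2), a discharge record holds up to 30 secondary diagnoses, so old disease can be coded at an unrelated admission.

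**2. The plan's own figure.** The protocol gives no background rate for narcolepsy, coronary artery disease or heart failure. The nearest 365-day example is arrhythmia in Table 2: rate 0.02 per person over 365 days, IRR 2, two-sided alpha 0.05, power 80%, and 1,178 per cohort.

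n = (1.960 + 0.842)² × (λ0 + λ1)/(λ1 − λ0)² = 7.849 × 0.06/0.0004 = 1,177.3, rounded up to 1,178. The plan's figure reproduces, and the look-back question does not affect that arithmetic.

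**3. Inputs the documents do not give (assumptions).** Let f be the share of counted unvaccinated events that are old disease, varied from 10% to 50%. Let d be the rate of counted old disease in the vaccinated relative to the unvaccinated after weighting, where d = 1 means equal re-recording.

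**4. Incidence rate.** If the person-time of the people who should have been excluded is small, the reported unvaccinated rate is the true rate divided by (1 − f). That is a factor of 1/0.90 = 1.11, 1/0.75 = 1.33 and 1/0.50 = 2.00 at f = 10%, 25% and 50%.

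**5. IRR.** Observed IRR = (1 − f) × true IRR + f × d. With d = 1, observed IRR − 1 = (1 − f) × (true IRR − 1). The last two columns carry the diluted IRR through the Table 2 formula with the counted rate held at 0.02. Power is Φ[(λ1 − λ0)/√((λ0 + λ1)/1,178) − 1.960].

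| f (d = 1) | True IRR 2 reads | True IRR 3 reads | n per cohort (true IRR 2) | Power at 1,178 (true IRR 2) |
|---|---|---|---|---|
| 0% | 2.00 | 3.00 | 1,178 | 80% |
| 10% | 1.90 | 2.80 | 1,406 | 73% |
| 25% | 1.75 | 2.50 | 1,919 | 59% |
| 50% | 1.50 | 2.00 | 3,925 | 34% |

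If instead the truly incident rate stays at 0.02 and old disease comes on top, the three larger sample sizes are 1,265, 1,439 and 1,963.

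**6. Direction when re-recording differs (f = 25%).**
- True IRR 1, d = 1: 1.00, no bias.
- True IRR 1, d = 1.25: 0.75 + 0.3125 = 1.06.
- True IRR 1, d = 2: 0.75 + 0.50 = 1.25.
- True IRR 1, d = 0.8: 0.75 + 0.20 = 0.95.
- True IRR 2, d = 3: 1.50 + 0.75 = 2.25.

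The observed IRR exceeds the true one whenever d is greater than the true IRR.

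**The case against.** The best defence is that a 12-month clean window is a legitimate choice for coronary artery disease and heart failure. Both can recur or worsen, and the rule's stated aim is to find new events, which need not mean first-ever disease. An any-time exclusion would remove many people from the at-risk set in a study of high-risk adults, and its reach would depend on how much history each source holds. This stands, and it is why the all-history rule should not simply replace the 12-month rule for those outcomes. It does not help narcolepsy.

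Second, section 9.9 describes chronically managed patients with frequent encounters, which should limit year-long gaps in coding. This also stands in part: the miscounted group may be a minority, and the documents do not say how large it is.

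Third, outcome algorithms are left to the SAP, and section 9.7.4 mentions narrow and broad algorithms and negative control outcomes. A SCRI analysis may also be considered for atrial fibrillation. These address code choice, bias in general, or a short acute window. None promises a longer look-back, and the exclusion rule itself is fixed in the protocol.

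Two stronger readings are tempting. A reader might infer that the IRR is always pulled towards 1. The documents do not support that: section 9.9 admits that differential ascertainment is possible, and under section 9.1.1 only the unvaccinated must have a vaccination record in the prior year. Equal re-recording therefore cannot be taken for granted.

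A reader might also construct a large false share. Taking prevalence of 10-30%, 15-30% of those uncoded in a year, 30-50% of these re-coded in the next, and 2% true incidence gives 0.0045/(0.0045 + 0.018) = 20% up to 0.045/(0.045 + 0.014) = 76%. Every input is assumed, the top figure needs all the extremes at once, and such values cannot describe narcolepsy.

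**Conclusion.** The concern holds in limited form. For chronic outcomes other than type 1 diabetes, the 12-month rule does not meet its own stated purpose, because old disease left uncoded for a year can be counted as incident. Narcolepsy is the clearest case, since the protocol's reasoning for type 1 diabetes applies to it directly. For coronary artery disease, heart failure and chronic arrhythmia, the gap is real but the choice of primary rule is partly a trade-off.

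Reported rates are inflated as long as people with old disease are re-coded faster than new disease arises, which is likely when incidence is low. The IRR is attenuated only if re-recording is equal and the true IRR is not 1; at a true IRR of 1 with equal re-recording it is unbiased, and with unequal re-recording it can move either way. The 1.90-1.50 range for a true IRR of 2 rests on an assumed 10-50% share and d = 1. The sample-size and power figures borrow the arrhythmia example and are illustrative only.

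**What to change.** 1. In section 9.2.2, extend the any-time exclusion (all available history) to narcolepsy, in the same words as for type 1 diabetes.
2. For coronary artery disease, heart failure and chronic arrhythmia including atrial fibrillation, prespecify a first-ever analysis with all-history exclusion and report it beside the 12-month analysis. The latter keeps recurrence and worsening in people with older disease.
3. Report, by cohort and data source, how many 12-month cases the all-history rule would have removed. This replaces the assumed f and d with observed values.

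The change is cheap. The type 1 diabetes rule already requires history older than 12 months, so extraction needs only additional outcome codes over the same period. For France the protocol states that "SNDS captures healthcare data from 2006 onwards". For SIDIAP, "The database captures healthcare data collected since January 2006". VID ambulatory records run from 2009 (section 9.4.2), and section 9.4.1 describes the UK general practice records as life-long. Section 9.4.4 mentions historic EpiChron data without giving its depth.

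The costs are fewer people at risk in the first-ever analyses and a look-back length that differs by source. Since estimates are made within source and then pooled (section 9.7.3.3), the second cost can be handled by stating the available history for each source.
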